6.4.3.2 Secondary Objectives Analyses

The effect of PF on BP Control

Our main clinical outcome is the proportion of patients with adequate BP control (<140/90 mmHg) at 12 months in the implementation vs. UC phase. BP control will be treated as a dichotomous outcome variable in this analysis; any patients with missing follow-up BP data will be assumed to have inadequate BP control. To examine the difference in BP control rates between the implementation and UC phases, we will utilize a generalized linear mixed model (GLMM) to assess the PF effect. A Poisson regression model will be used to predict BP control specifying a fixed effect for time, a fixed effect for treatment and a time by treatment interaction. Random effects will be specified for person and practice to account for the clustered nature of the dataset (observations within person and people within practices). As a sensitivity analysis, we will also assess an alternate definition of BP control (< 130/80 mmHg) indicated by the new hypertension guidelines. In exploratory analyses, will examine the intervention effect on BP reduction at 12 months, treated as a continuous variable. An additional sensitivity analysis will be conducted using GLMM to evaluate the effect of PF on BP reduction. We will test the treatment X time interactions in a random effects linear regression model to determine the time-specific differences BP reduction attributable to PF at the end of the implementation phase.

Randomization of the stepped-wedge design should obviate the need for adjustment, but in the case of imbalanced in baseline covariates; these will be included as necessary in adjusted analyses. All tests will be two-sided with $\alpha=0.05$ for comparison between the implementation and UC phases. Maximum likelihood estimation of mixed-effects models will be used to account for missing data; in the context of a mixed-effects model, this is equivalent to an assumption of data that are missing at random (MAR); we will conduct sensitivity analyses assessing this assumption. We will also compare participants with and without missing values with respect to baseline and practice characteristics. If differential patterns emerge, we will consider the use of multiple imputation and/or inverse probability weighting to adjust for missing data. Analyses will be conducted using Stata, SAS, and R.

Associations between rates of BP control and implementation fidelity will be evaluated using structural equation modeling methods. We will estimate a path model using maximum likelihood estimation to investigate relationships between BP control and implementation fidelity. Implementation fidelity will be identified as individual and simultaneous predictors of BP control. Practice-, staff-, and patient-level variables, which may influence level of implementation fidelity, will also be included in the model. In addition to the direct effects of each variable, the indirect effects from each variable to BP control via mediator variables will be estimated as the product of component direct effects and tested using bootstrapped 95% confidence intervals. Structural equation modeling analyses will be conducted using R and fit indices will be evaluated to ensure model fit.

The effect of PF on medication adherence

We will estimate similar models as BP control with PDC, calculated from available pharmacy records, as the outcome. A GLMM model using maximum likelihood estimation will be utilized to estimate the effect of PF on medication adherence with fixed effects specified for treatment phase, time, and the treatment by time interaction. We will apply any necessary transformations to the PDC outcome to improve the approximation to normality, and explore alternative regression strategies, such as rank regression and/or beta regression.

The effect of practice and individual-level moderators on implementation fidelity of ALTA

Using validated surveys (described above), we will explore potential practice-, staff- and patient-level moderators, assessing interactions between the PF strategy, level of implementation fidelity and modifiers. Potential moderators of the association between PF and implementation fidelity of ALTA will be evaluated using structural equation modeling methods. We will determine potential moderators by examining the PF x moderator interaction effects. Fit indices will be evaluated for all models to ensure adequate model fit.

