6.4.2 Sample Size Considerations

Power calculations are based on the clinical outcome of BP control using our prior work implementing the ALTA model in a community-based clinic. In the former trial, we found a significant improvement in attainment of BP control at 6 months among patients randomized to the intervention group compared to the UC group (51% vs. 29%, $p=.03$). We expect a similar group difference of a 20% increase in BP control between the implementation and UC phases in the current study. Calculations of achieved power were estimated with a stepped-wedge design using Power Analysis and Sample Size (PASS) software program. The power calculations show that we can recruit 10 sites and 700 patients and have at least 80% power to detect a more conservative 15% difference in BP control between the UC and implementation phases for intraclass correlation coefficients (ICCs) ranging from 0.01 to 0.05. Using our original estimate of a 20% difference in BP control, we would have over 90% power to detect a difference between the UC and implementation phases with 10 sites and 700 patients.

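### The blood-pressure-control and PDC models combine treatment phase, time and their interaction without defining time or naming the term that gives the powered implementation-versus-usual-care difference

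*Combined protocol and SAP*

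**What the plan says.** Section 6.4.3.2 gives the aim for BP control: "To examine the difference in BP control rates between the implementation and UC phases". The model is a Poisson mixed model "specifying a fixed effect for time, a fixed effect for treatment and a time by treatment interaction", with random effects for person and practice. On testing it says: "All tests will be two-sided with $\alpha=0.05$ for comparison between the implementation and UC phases". No coefficient or contrast is named as that comparison, and time is not defined as calendar period, time since start of implementation, or baseline/12 months.

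The PDC model in the same section is built "with fixed effects specified for treatment phase, time, and the treatment by time interaction", again with no deciding term. The tertiary model in 6.4.3.3 lists the same three terms plus a control-group indicator.

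The plan names a deciding term in two other places, and both times it is the interaction. One is the model in 6.4.3.1 linking fidelity to clinical outcomes, where time is coded 0 and 12 months and a UC/PF group is the between-patient factor. The other is the additional continuous-BP analysis in 6.4.3.2: "We will test the treatment X time interactions in a random effects linear regression model".

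Section 6.4.2 powers a single average difference. It claims "at least 80% power to detect a more conservative 15% difference in BP control between the UC and implementation phases" for ICCs of 0.01 to 0.05, and for the 20-point effect that "we would have over 90% power to detect a difference between the UC and implementation phases with 10 sites and 700 patients". It mentions no interaction.

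**The concern.** In this design every practice starts in usual care and later crosses over (section 5.1 and Figure 1), so treatment is the phase a practice is in. A treatment-by-time interaction is the natural effect measure in a parallel two-arm trial with a baseline and a follow-up. In a stepped wedge with calendar time it asks a different question, namely whether the effect changes over time. It is zero when PF has the constant 15- or 20-point effect used for the power statement.

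Once the interaction is in the model, the treatment coefficient is the effect at the point where time equals zero. If time is counted from the start, that is a point at which no practice is in implementation, so the coefficient is an extrapolation with a large standard error.

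Two analysts could both follow the text, choose different terms or time origins, and report opposite conclusions on the main clinical outcome, with the choice made after the data are in hand.

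**Working it through.** **Inputs from the documents.** 10 sites, 700 patients, differences of 15 and 20 points, ICC 0.01 to 0.05, and 29% control under UC in the former trial (6.4.2); two-sided alpha 0.05 (6.4.3.2).

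**Assumptions.** UC rate 29%. Five waves of two practices: Figure 1 shows five cohorts, while the text of 5.1 gives four waves of two, which makes only eight sites. Six periods. 700 observations spread evenly, so m = 700/(10 × 6) = 11.67 per practice-period. Identity scale, no person random effect, constant effect.

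**Method.** Generalised least squares on practice-period means. With p = (0.29 + 0.44)/2 = 0.365, total variance is 0.365 × 0.635 = 0.2318. The between-practice part is ICC × 0.2318 and the within-practice part is (1 − ICC) × 0.2318. For practice i, V = (within/m)·I + between·J, and the covariance of the estimates is (Σ Aᵢ′V⁻¹Aᵢ)⁻¹, where Aᵢ holds the model terms. Power = Φ(d/SE − 1.96) + Φ(−d/SE − 1.96).

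**Step 1: the plan's own figure.** Without the interaction:
- 15 points: SE 0.0545 (ICC 0.01) and 0.0592 (ICC 0.05). Then 0.15/0.0545 = 2.75 gives 79%, and 0.15/0.0592 = 2.53 gives 72%.
- 20 points: 95% and 92%, in line with the plan's claim of over 90%.
- With 1,400 observations (two per patient, treated as independent within practice), 15 points gives 92-96%, depending on ICC and on how the variance is split.

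The claim of at least 80% for 15 points therefore depends on observations per period, number of steps and base rate, none of which is given for the PASS calculation.

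**Step 2: treatment coefficient for 15 points, 700 observations.**

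| Model | SE, ICC 0.01 | SE, ICC 0.05 | Power |
|---|---|---|---|
| No interaction | 0.0545 | 0.0592 | 79%, 72% |
| Interaction, linear time from first period | 0.0914 | 0.0937 | 38%, 36% |
| Interaction, period effects, time from first period | 0.1360 | 0.1388 | 20%, 19% |
| Interaction, time centred at mid-study (linear or period effects) | 0.0545 | 0.0592 | 79%, 72% |

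The SE ratios against the first row are 1.68 and 1.58 (linear), and 2.50 and 2.34 (period effects). For 20 points, counting from the first period gives 30-58%, against 92-95% without the interaction. Centring restores full power because, at the midpoint of this symmetric design, the coefficient is the average effect.

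**Step 3: interaction test.** With calendar time and a constant effect the true interaction is zero, so the test rejects at alpha, 5%. A simulation of 1,500 Poisson fits with robust SE (29% versus 44%, no clustering, linear time) gave 4.7%. The treatment coefficient in those fits was significant in 46% with the interaction and 85% without.

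**Step 4: baseline/12-month reading.** Section 5.2.2 measures BP in the pre- and post-intervention periods. If every patient's baseline is UC and 12 months is implementation, a patient's rows are (intercept, time, treatment, interaction) = (1, 0, 0, 0) and (1, 12, 1, 12). The last three columns are proportional, so the matrix has rank 2 with four terms and the effects cannot be separated.

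**Step 5: an alternative that keeps the interaction.** With period-specific effects, only the four periods that contain both phases are estimable. Their pre-specified average has SE 0.0555 and 0.0601, so power 77% and 70%, close to the 79% and 72% of the single-coefficient model.

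**The case against.** The plan does state its target, the difference between phases, and sets alpha for that comparison. Nothing in 6.4.3.2 tells the analyst to decide BP control on the interaction. It is named only for the fidelity association and for a continuous-BP sensitivity analysis that openly seeks time-specific differences. The low power for the treatment coefficient also follows from where time zero is placed: centred at mid-study, nothing is lost. On a two-group, 5-versus-5 baseline/12-month reading, the interaction would be the treatment effect itself, with roughly 50-89% power for 15 points. Deleting the interaction is not the only remedy, and BP control is a secondary outcome.

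Most of this stands, and it limits the point. A reader might infer that neither term can ever be the average difference, or that the treatment coefficient is always well under 80% power. The documents do not support that, because they leave the coding of time open.

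It does not close the gap. The BP control model neither centres nor defines time. The only coding in the documents, 0 and 12 months in 6.4.3.1, is uncentred. The favourable parallel-group reading needs practices fixed in one arm, which the stepped wedge does not have.

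**Conclusion.** The point holds in conditional form. Sections 6.4.3.2 and 6.4.3.3 list the model terms but leave open both the meaning of time and the deciding contrast, while 6.4.2 powered one average difference. Across codings compatible with a stepped wedge, the test of a constant 15-point effect ranges from not estimable, through about 5% (interaction) and 19-38% (treatment coefficient, time from the first period), to the full 72-79% of the assumed design.

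These figures rest on five waves of two practices, six periods, 700 observations, a 29% UC rate and an identity-scale approximation without a person effect.

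A reader might also infer that the stated 80% power is wrong, since even the clean model gives 72-79% here. That does not follow: the PASS inputs are not reported, and 1,400 observations would give 92-96%. No power is stated for PDC or the tertiary outcomes, so for them the gap is one of definition only.

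This should be fixed. BP control is secondary to implementation fidelity, but it is the outcome on which the sample size rests.

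**What to change.** - In 6.4.3.2, for BP control and PDC, define time as calendar period. State that the PF effect is the single treatment-phase coefficient (implementation versus UC), tested at two-sided 0.05, from a model without the interaction. A pre-specified average of the estimable period-specific effects is an acceptable alternative with almost the same power.
- Keep the treatment-by-time interaction as a labelled secondary check of whether the effect varies over time.
- In 6.4.3.3, name one deciding contrast in the same way, saying how the control-group indicator enters it.
- The time-specific continuous-BP analysis may stay as an exploratory sensitivity analysis, with a sentence that it is not the test of the average PF effect.

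The cost is SAP wording only, with no new data. The small downside is that variation of the effect over time becomes a secondary question.

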5.1 General Design

Using a stepped-wedge cluster randomized control trial design, this study will evaluate the effect of a tailored PF strategy on the implementation of Advancing Long-term Improvements in Hypertension Outcomes through a Team-based Care Approach (ALTA), our systems-level approach to improving medication adherence and BP control, among patients with uncontrolled HTN receiving care in 10 safety-net practices in New York.

Using a mixed-methods approach, this study will be conducted in two phases: (1) a pre-implementation phase where we will refine the PF strategy, based on the Consolidated Framework for Implementation Research (CFIR) to facilitate implementation of ALTA at the practices and (2) an implementation phase, guided by Proctor's Implementation Outcomes Framework (IOF). The primary aim of the implementation phase is to evaluate, in a stepped-wedge cluster randomized trial, the level of implementation fidelity (e.g., degree to which a program is delivered, as intended) of ALTA because of the tailored PF strategies. The secondary aims are to compare the effects of PF versus usual care (UC) on BP control and medication adherence in 10 safety-net primary care practices and patients with uncontrolled HTN who are non-adherent to their antihypertensive medications. We will also explore the potential moderating factors at the practice and individual levels (e.g., organizational capacity to change, evidence-based practice attitudes) that influence level of implementation fidelity of ALTA at the practices. We will also explore the impact of ALTA on the patient-provider relationship (i.e., relationship commitment, patient-provider trust, and patient anxiety in the interaction), and determine whether any changes to the relationship also affect patients' BP control and medication adherence.

As shown in Figure 1, each participating practice will start with the UC phase and are block-randomized into four waves, with two sites per wave. The UC phase will be followed by the pre-implementation phase of 6 months, during which facilitators will conduct a practice evaluation (e.g., workflow analysis, environmental scan) based on CFIR, refine the PF strategies that will be used in the implementation phase, and train staff in the ALTA model. Following this period, sites will implement ALTA with the assistance of the facilitator for 12 months, with a 3-month follow-up period for outcome assessment.

Figure 1. Stepped wedge design of ALTA implementation

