5.1.1 Study Duration (if applicable)

The study duration is 24 months. During the UC phase, patients at the sites will receive standard HTN care delivered by their primary care providers for the first 3 months. The pre-implementation phase will be the following 6 months of the trial to refine the PF strategy that will be used during the implementation phase. The implementation phase will be 12 months and there will be two study visits: consent/baseline and 12-month follow-up.

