6.3.4 Recruitment, Enrollment and Retention

Practice clinical and non-clinical staff will be recruited through study team attendance at the monthly staff meetings, email communications that describe the project including the overarching goals and what is expected of participants, and in-person or virtual meetings with the practices.

We will recruit approximately 500 patients across the practices who meet the following eligibility criteria (described above). Several strategies will be used to maximize the number

of eligible patient participants recruited per practice as described below. Signed informed consent will be obtained from participants who meet the study eligibility criteria.

Since this is a clinic wide initiative, we are broadening our eligibility criteria to include patients of all race and ethnicities, and not be exclusive to Latinx patients (this is also reflected in the change to our project name). We will still recruit a random sample of 70 patients per clinic that receive care in the 10 safety-net practices to participate in the surveys to assess our tertiary outcomes. Of this sample, 30 will be randomly selected to participate in an exit interview. Patients will be randomly selected from a list of patients who receive care in the clinics and have been exposed to the ALTA project. The same recruitment strategies will be employed to recruit 300 patients who receive care in the clinics and met eligibility for ALTA but did not ultimately participate in the project. All patients will provide written informed consent prior to participating in the study.

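### In section 6.4.3.2 no usual-care BP reading is concurrent with a 12-month reading, so the BP-control contrast cannot be separated from calendar time, and the power in 6.4.2 does not apply to it

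*Combined protocol and SAP*

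**What the plan says.** **Outcome and model.** Section 6.4.3.2 takes BP control at 12 months, implementation versus UC phase, as the main clinical outcome. It fits a Poisson mixed model "specifying a fixed effect for time, a fixed effect for treatment and a time by treatment interaction", with random effects for person and practice. Time is not defined there. The only coding in the document is months 0 and 12, given in 6.4.3.1 for the fidelity analysis. On adjustment, 6.4.3.2 says "Randomization of the stepped-wedge design should obviate the need for adjustment" and then allows for imbalanced baseline covariates. Testing is at two-sided 0.05.

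**Readings.** Section 5.2.2 uses one summary per period: the mean of the two latest EHR readings before the intervention, and the same after it. Section 5.1.1 says "there will be two study visits: consent/baseline and 12-month follow-up".

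**Schedule.** Section 5.1 says practices are "block-randomized into four waves, with two sites per wave". It continues: "The UC phase will be followed by the pre-implementation phase of 6 months". Twelve months of ALTA and a 3-month outcome period come next. Figure 1 shows five cohorts starting one quarter apart.

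**Power.** Section 6.4.2 claims to "have at least 80% power to detect a more conservative 15% difference in BP control between the UC and implementation phases" with 10 sites, 700 patients and ICCs of 0.01 to 0.05, and over 90% for 20 points. It cites a stepped-wedge calculation in PASS without giving periods or cell sizes. Section 6.3.4 says "We will recruit approximately 500 patients across the practices", yet keeps 70 per clinic.

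**The concern.** A stepped wedge separates the intervention from calendar time because, in some periods, some sites are treated while others are not. Here each site's 12-month reading comes at least 18 months after its UC phase ends (6 months of pre-implementation plus 12 of ALTA), while the whole stagger between the first and last cohort is 12 months. The last site has left UC before the first site reaches 12 months.

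Any change in BP control over calendar time is then credited to practice facilitation. The protocol itself mentions COVID-19 constraints, new hypertension guidelines and other quality-improvement initiatives at the sites. BP control is a secondary outcome, but it is the sole basis for the sample size.

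**Working it through.** **1. Calendar.** Number the quarters in Figure 1 from 1 to 16. For cohort c = 1 to 5:

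| Phase | Quarters | Cohort 1 | Cohort 5 |
|---|---|---|---|
| UC | 2 to 1+c | 2 | 2–6 |
| Pre-Imp | 2+c, 3+c | 3–4 | 7–8 |
| Intervention | 4+c to 7+c | 5–8 | 9–12 |
| Outcome evaluation (OE) | 8+c | 9 | 13 |

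Cohort 1's durations (3 + 6 + 12 + 3 = 24 months) match 5.1 and 5.1.1. The last UC quarter is 6. The first 12-month quarter is 8 (last intervention quarter) or 9 (OE).

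**2. Can the effect be estimated from a UC and a 12-month reading?**
- *Time coded 0/12.* Time/12, treatment and their product are the same column. With an intercept the rank is 2 of 4.
- *Categorical calendar quarter.* Last UC plus 12-month readings occupy ten distinct quarters. The treatment column equals the sum of the five 12-month quarter indicators, so the rank is 10 of 11.
- *Linear calendar trend.* Estimable, with power for 15 points of about 13% to 40% at 1,400 readings.
- *No calendar term.* Estimable, but a before-after contrast.

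**3. Size of the confounding with no calendar term.** From the last UC quarter to the last intervention quarter is 6 quarters. Take 70 readings per site and phase, a true rate of 29% and no effect. Then SE = √[2 × 0.29 × 0.71 × (1 − ICC)/700] = 0.0241 at ICC 0.01 and 0.0236 at 0.05. An assumed rise of 0.5 points per quarter shifts the contrast by 3 points, and the rejection probability is about 24%. A rise of 1 point per quarter shifts it by 6 points, and the probability is 70% to 72%.

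**4. The plan's own power figure.** Inputs: 10 sites, 700 patients, ICC 0.01 to 0.05, two-sided 0.05. I assume 29% in UC, the control rate of the prior trial. The model has a random site intercept and categorical periods. For 29% versus 44%, s² = 0.365 × 0.635 = 0.2318. Within a site, a cell mean of m readings has residual variance s²(1 − ICC)/m, and cells share covariance ICC × s². Power = Φ(δ/SE − 1.96).
- Textbook layout, 5 steps of 2 sites, 6 periods, m = 70/6 = 11.67. For 15 points SE = 0.0545 to 0.0592, power 79% to 72%. For 20 points SE = 0.0552 to 0.0600, power 95% to 92%.
- With m = 14, power for 15 points is 85% to 79%. With control-rate variance at m = 11.67 it is 83% to 77%.

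The over-90% figure reproduces. The at-least-80% figure is reachable under some variants but cannot be confirmed without the PASS inputs.

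**5. Power on the actual calendar, categorical quarters, 15 points.**

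| Readings used | Readings | Power (ICC 0.05 to 0.01) |
|---|---|---|
| Last UC + 12-month | any | not estimable |
| Last Pre-Imp + last intervention quarter | 700 | 20–36% |
| Last Pre-Imp + last intervention quarter | 1,400 | 23–52% |
| All UC + intervention + OE | 700 | 28–30% |
| All UC + intervention + OE | 1,400 | 48–51% |
| All UC + intervention + OE, 70 per site-quarter | 5,600 | about 96% |

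The last three rows use 80 site-quarters: 2 sites × (15 UC + 20 intervention + 5 OE). For 700 readings m = 8.75 and SE = 0.104 to 0.109; for 1,400, m = 17.5 and SE = 0.076 to 0.079; at m = 70, SE = 0.040. UC and intervention coexist only in quarter 5 (cohort 1 treated; cohorts 4 and 5 in UC) and quarter 6 (cohorts 1 and 2 treated; cohort 5 in UC). All rows treat readings as independent given site, so the last is an upper bound.

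**The case against.** **Time is already in the model.** True. A reader might infer that the plan has no time term and that this makes the effect inestimable. The documents do not support that. A fixed effect for time is named; the defect is that it is undefined. Leaving calendar time out makes the contrast estimable but confounded. Aliasing arises when categorical quarters are added, or when 0/12 time is entered beside phase.

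**Some readings do overlap.** Also true. The documents never say whether Pre-Imp readings count as pre-intervention. If they do, and the 12-month reading is the last intervention quarter, cohorts 1 and 5 share quarter 8 and the effect is estimable, with the 20% to 52% power shown above. If every Pre-Imp quarter is used as untreated, 1,400 readings give 83% to 86%. But staff are trained in ALTA during Pre-Imp, and 6.4.3.2 names UC as the comparator. So the stronger reading, that this trial can yield no stepped-wedge estimate at all, fails. The two-reading contrast as described still lacks a concurrent comparison.

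**The power statement may be right.** For a textbook stepped wedge it is plausible, so it cannot be called false. What stands is that it is not matched to these readings and this model.

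**The sentence on adjustment concerns covariates.** Mainly so. It should still not be left to cover calendar time, which randomizing the wave order does not balance between phases.

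**Figure 1 was read from extracted table columns.** The non-overlap does not depend on exact columns: an 18-month gap exceeds a 12-month stagger.

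**Conclusion.** The point holds as headed. Followed literally, 6.4.3.2 gives either an aliased treatment effect (0/12 time or categorical quarters) or a before-after comparison that absorbs secular change. With no true effect, assumed rises of 0.5 and 1 point per quarter would be declared effects about 24% and 70% of the time.

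The stated power belongs to a different layout. On the actual calendar with categorical quarters it ranges from undefined (UC and 12-month readings only), through 28% to 51% (700 to 1,400 readings over all UC, intervention and OE quarters), to about 96% at best with 70 independent readings per site-quarter. Whether the restated power ends above or below 80% therefore depends on how many EHR readings can be used.

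These figures assume the Figure 1 timing, a 29% UC rate, a constant effect, the ICC range in 6.4.2 and a normal approximation on the probability scale in place of the Poisson model. The conclusion concerns BP control, not the primary fidelity outcome.

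**What to change.** 1. In 6.4.3.2, define time as categorical calendar quarter. Code treatment by site and quarter: UC = 0, after ALTA start = 1, Pre-Imp quarters excluded or given their own term. Keep site and patient random effects. Use EHR BP readings from all UC and intervention quarters for the patients whose records may be used.
2. Do not use the treatment-by-time interaction as the test. State that randomization does not remove the need to adjust for calendar time.
3. Report the effect over implementation quarters as the randomized estimate, and label 12-month versus UC as before-after. In quarters 5 and 6 the treated cohorts are in their first 6 months of ALTA, so the direct concurrent evidence concerns early exposure.
4. Reconcile four waves of two sites (4 × 2 = 8) with the five cohorts and 10 sites; the 3-month UC phase in 5.1.1 with UC of 3 to 15 months in Figure 1; and approximately 500 patients with 700. Then restate the power in 6.4.2 with periods, readings per site-quarter and control rate.

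**Cost.** Protocol and SAP wording, a new power run and possibly a lower stated power. EHR BP data are already requested in 6.1.4, but that section describes de-identified, aggregate analysis, and 6.3.6 limits the 12-month chart review to consenting patients. A patient-level quarterly extraction must fit those permissions or have them amended.
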